5. OBJECTIVES

5.1 Primary Objective

To evaluate the sensitivity, specificity, positive and negative predictive value of metabolomic biomarkers in exhaled breath samples to identify acute breathlessness, defined as one or more of (i) patient defiend acute breathlessness and/or a (ii) 1 unit increase in Extended Medical Research Council breathlessness score (eMRC)

Page 14 of 46

- Recruitment in to the acute breathlessness group will be according to the following defined primary diagnoses in the discovery phase as defined by the treating physician:
 - (i) Acute Heart failure (n=55-100), (ii) Community acquired pneumonia (n=55-100), (iii) Adult exacerbations of asthma and COPD (n=110-200) and (iv) paediatric exacerbations of acute childhood wheeze and/or confirmed asthma (n=50-100). Additionally age/home environment matched adult/spouse/sibling/parent control subjects (n=55-150 adults/50 children).

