5.2 Secondary Objectives

- To replicate selected metabolomic breath biomarker panels of acute breathlessness using a combination of both (i) discovery technologies (including GC-MS) and (ii) point of care auto tuned breath sensing devices (including linear IMS, CMS, PTR-MS).
- To evaluate the primary endpoint stratified by breathlessness as follows (i) change in eMRC by 1
 unit, (ii) patient defined breathlessness and (iii) 100 mm visual analogue score for breathlessness
- To discover and replicate metabolomic breath biomarkers that differentiate (i) Acute Heart failure,
 (ii) Community acquired pneumonia, (iii) Adult exacerbations of asthma and COPD
- To quantify the level of clinical uncertainty in the primary diagnosis using a 100 mm visual analogue scale and independent clinical adjudication of case notes blinded to the following blood biomarkers (i) CRP (ii) blood eosinophils (iii) BNP (iv) Troponin-I but not clinical history and chest X-ray.
- To identify and discover metabolomic breath biomarkers of acute childhood wheeze and or confimed asthma.

To clinically validate metabolomic breath biomarkers generated above using a combination of existing pathology markers e.g. BNP, CRP, blood eosinophils and troponin- I and other clinical relevant prognostic scoring tools e.g DECAF, CURB65 and Heart failure risk calculator http://www.heartfailurerisk.org/^[19]

- Replication of acute breathlessness biomarkers will be according to the following predefined primary diagnoses in the replication phase:
 - (i) Acute Heart failure (n=55-100),(ii) Community acquired pneumonia (n=55-100), (iii) adult exacerbations of asthma and COPD (n=110-200),(iv) paediatric exacerbations of acute childhood wheeze and confirmed asthma (n=25-100),(v) age/home environment matched adult/spouse/sibling/parent control subjects (n=55-75 adults/25 children)
 - 5.3 Exploratory End Points (where applicable)
 - 1) To evaluate the dynamic profile of breath biomarkers during (i) the acute state, (ii) in the recovery state post exacerbation.

Page 15 of 46

- 2) To evaluate the relationship between breath metabolomic biomarkers and health status/ functional measures:
- Health status measures
- Physical performance
 - 3) To evaluate the relationship between metabolomic breath biomarkers and clinical outcomes including (i) hospital readmission at time points up to 2 years (ii) response to standard clinical therapy and (iii) death.

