10. STATISTICS

participants.

10.1 Description of Statistical Methods (Detailed statistical anad analytical methods are outlined in the MRC-EMBER data analysis plan).

Primary Analysis

For the primary analysis the outcome is a nominal variable with levels (1) Acute breathlessness (2) Recovery form acute breathlessness. The relationship between the primary outcome and the metabolomics biomarkers in exhaled breath sample will be modelled using multinomial logistic regression. Acute

Page 32 of 46

breathlessness will be defined as one or more of (i) patient defined acute breathlessness and/or a (ii) 1 unit increase in Extended Medical Research Council breathlessness score (eMRC). In addition to metabolomics markers the following independent variables will be included in the model: age, sex, standard acute care pathology markers blood eosinophils, BNP, CRP, Troponin-I, canonical VOCs extracted from breath analysis and where relevant validated co morbidity scores (e.g. Charlson comorbidity score).

Adjudication

All acute/healthy adult patients' notes will be sequentially divided. These will then be reviewed and independently adjudicated by two independent respiratory consultants, blinded to admission bloods and diagnosis. The panel will independantly decide the primary diagnosis as well as mark their level of certainty on a 100 mm VAS scale. The panel member will then be able to review imaging, ECGs, and ABGs but not blood results. Results will be both -validated by separate panel member to ensure agreement using Bland-Altman and Correlations and within rater agreement will be assessed by replicate analysis of at least 20 cases 4 weeks apart.

Binary logistic regressions will be utilised to assess associations between VOCs and acute disease. ROC curves will be produced for individual predictors in the primary analysis. Additional techniques for multi variate analysis including but not limited to cluster analysis, structural equation modelling and topological data analyses will be applied where relevant. Tables of descriptive statistics will be compiled for all key variables. All analysis will be performed using SAS 9.4 http://www.r-project.org/.

Secondary Analysis

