For the secondary analysis pertaining to other definitions of acute breathlessness, visual analogue breathlessness scores (100mm) and a 1 unit increase in the extended medical research council analysis outlined above for the primary endpoint will be performed based upon stratification of breathlessness type.

For the secondary analyses pertaining to discovery of breath metabolomics markers the outcome is a nominal variable with levels (1) Acute Heart failure (2) Community acquired pneumonia 3) Adult exacerbations of asthma/COPD (both in combination and considered individually) and (4) Acute exacerbations childhood wheeze and confirmed asthma in children. The relationship between the primary outcome and the metabolomics biomarkers in exhaled breath sample will be modelled using multinomial logistic regression and ROC curves. In addition to metabolomics markers the following independent variables will be included in the models where necessary (improve model fit): age, sex, validated co morbidity scores such as the Charlson score, indicator disease risk scores such as the CURB-65 pneumonia score, DECAF COPD exacerbation scores and treatments commonly used acutely for the indicator diagnoses.

Subsidiary Analysis

For subsidiary analyses modelling risk of re admission, death and length of stay we will utilise the following approaches

- Cox proportional hazards model will be fitted and competing risk models will be fitted for readmission. Logistic regression analysis will be used when looking at risk at particular time points for readmission.
- The number of exacerbation events will be modelled using Poisson or Negative Binomial regression.
- Relationship between death and breath biomarkers will be evaluated using a logistic regression model.

Page 33 of 46

For subsidiary analyses pertaining to dynamic profile of breath biomarkers during (i) the acute states (time points 1a), (ii) transition to the stable state (time point 1b) and (iii) in the chronic state 8-12 weeks post exacerbation (time point 2), a repeated measures model with a random intercept and random effect for time will be fitted, the random effects will be fitted for each patient. For the repeated measures mixed model an unstructured covariance will be assumed.

Other outcomes are exploratory and based around feasibility of an acute care platform for airways disease. Statistical analyses for these outcomes will be performed as appropriate for hypotheses derived in this exploration.

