21.2 Closed formula for logistics regression models

82 acutely breathless adults (asthma:35, community acquired pneumonia :16, COPD:26) and 17 healthy controls were utilised for the analysis.

A panel of 10 pre specified aldehyde biomarkers derived from GCMS analysis were supplied. The biomarkers were normalised to a common standard and were not background subtracted.

A closed formula from Hsieh et al, Statis med 1998, was utilised to calculate sample sizes from logistic regression models of the 10 aldehydes with acute breathlessness as the outcome measure. The sample size estimates are also relevant to acute class comparions vs. the sum of other acute classes.

The results of the analyses are outlined in the figure below (each BRI number annotates a specific aldehyde).

Based upon the sample size estimates we would have an 80% power at the 5 % significance level to detect an odds ratio of association of 1.2 for a given disease class with 55 patients per disease class. Given the fact that MRC EMBER seeks to discover and replicate breath VOCs amongst 5 adults classes (CAP, heart failure, COPD, asthma and healthy aged matched subjects).

We would require 110 patients per class – 550 patients across the program to achieve these aims.

Commented [CSB1]: This is not a complete sentence. There is a clause missing, or else the punctuation needs adjustment.

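### The only multivariable primary model fixes four blood markers beside the breath markers, so any multi-marker accuracy taken from it is that of breath plus blood

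*Protocol*

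**What the plan says.** Section 5.1 states the primary objective: "To evaluate the sensitivity, specificity, positive and negative predictive value of metabolomic biomarkers in exhaled breath samples to identify acute breathlessness". Blood markers are not part of it.

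Section 10.1, Primary Analysis, sets a logistic model with two outcome levels, "1) Acute breathlessness (2) Recovery form acute breathlessness". Beside the breath markers, "the following independent variables will be included in the model: age, sex, standard acute care pathology markers blood eosinophils, BNP, CRP, Troponin-I". Canonical VOCs and, where relevant, a comorbidity score are also listed. The four blood markers carry no such condition.

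The same section names two other analyses: "ROC curves will be produced for individual predictors in the primary analysis", and "Binary logistic regressions will be utilised to assess associations between VOCs and acute disease". No covariates are listed for the second.

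Elsewhere blood is kept apart from breath:

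- The secondary disease-class model does not list the four blood markers. Its covariates are "included in the models where necessary (improve model fit): age, sex, validated co morbidity scores such as the Charlson score", followed by disease risk scores and treatments.
- Section 5.2 gives pathology markers their own secondary role: "To clinically validate metabolomic breath biomarkers generated above using a combination of existing pathology markers".
- Appendix C (21.2) derives "sample sizes from logistic regression models of the 10 aldehydes with acute breathlessness as the outcome measure", with no blood terms mentioned. Appendix C (21.3) sets an 80% target for sensitivity, and the same for specificity, as the mark of a useful biomarker.

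**The concern.** The objective asks how well breath identifies acute breathlessness. The stated multivariable model answers how well breath and four blood tests do so together. Two things follow.

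1. Attribution. A combined accuracy figure cannot be credited to breath. It could meet the 80% target largely or wholly through blood.
2. Interpretation of coefficients. Each VOC coefficient is conditional on blood markers that may move with the same acute event. A VOC sharing that signal may look weak in the model although it identifies acute breathlessness on its own.

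The study means to discover and replicate breath panels (section 4 and 5.2), so a panel accuracy that is really breath plus blood would be carried into the replication phase under the wrong name.

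**Working it through.** **The plan's own accuracy figures.** Appendix C (21.3) uses N = z² × 0.8 × 0.2 / (d² × share), with share 0.8 for sensitivity and 0.2 for specificity.

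- 95%, d = 0.05: 1.96² × 0.16 / (0.0025 × 0.8) = 307.3, and with 0.2, 1,229.3. Stated: 307 and 1,230.
- 90%, d = 0.05: 1.64² × 0.16 / 0.002 = 215.2, and / 0.0005 = 860.7. Stated: 215 and 861.
- 95%, d = 0.08: 1.96² × 0.16 / (0.0064 × 0.8) = 120.05, and with 0.2, 480.2. Stated: 120 and 480.

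All six reproduce. The 80% enters as the accuracy of a biomarker, and nothing in the calculation refers to blood.

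**Illustration of the joint model.** The documents give no accuracy for breath or blood and no correlation between them, so these are assumptions: one breath score and one blood score, normal with equal variance in both states, within-state correlation ρ from 0 to 0.7, and a cut-off where sensitivity equals specificity.

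- Shift in SD units from accuracy alone: δ = 2 × Φ⁻¹(accuracy). So 60% gives 0.507, 70% gives 1.049 and 80% gives 1.683.
- Joint separation: D² = (δb² + δc² − 2ρδbδc) / (1 − ρ²), with b for breath and c for blood. Joint sensitivity = specificity = Φ(D/2).
- Breath log odds ratio per SD: δb unadjusted, (δb − ρδc) / (1 − ρ²) adjusted for blood.

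Worked row, breath 70%, blood 80%, ρ = 0.5: D² = (1.100 + 2.833 − 1.765) / 0.75 = 2.89, and Φ(0.850) = 80.2%. Adjusted coefficient = (1.049 − 0.842) / 0.75 = 0.28, and 0.28 / 1.05 is about 0.26 of unadjusted.

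| Breath alone | Blood alone | ρ | Joint sens. = spec. | Adjusted / unadjusted breath coefficient |
|---|---|---|---|---|
| 50% | 80% | 0 | 80.0% | both zero |
| 60% | 80% | 0.3 | 80.0% | 0.00 |
| 70% | 80% | 0 | 83.9% | 1.00 |
| 70% | 80% | 0.3 | 81.3% | 0.57 |
| 70% | 80% | 0.5 | 80.2% | 0.26 |
| 70% | 80% | 0.7 | 80.1% | −0.24 |
| 80% | 70% | 0 | 83.9% | 1.00 |
| 80% | 70% | 0.3 | 81.3% | 0.89 |
| 80% | 70% | 0.5 | 80.2% | 0.92 |
| 80% | 70% | 0.7 | 80.1% | 1.11 |

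Three readings. The first row meets the 80% target with no breath signal. The 70/80 and 80/70 blocks give identical joint accuracy, so the joint figure cannot show which source carries it. The coefficient may be unchanged, attenuated, zero (when δb = ρδc) or reversed; when breath is the stronger source it hardly moves.

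**The case against.** The strongest reply is that the protocol never says the accuracy figures will be read from this model. Section 10.1 uses it to describe the relationship between outcome and breath markers, names single-predictor ROC curves as an accuracy output, and leaves detail to a separate data analysis plan. For a single VOC, such a curve is breath-alone accuracy, and the binary VOC regressions list no blood terms. If the canonical VOCs are composite scores, their individual ROC curves would even be panel accuracy. Section 4 also wants markers that add to conventional algorithms, which gives adjustment a rationale, and 10.2 calls the study exploratory.

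Much of this stands, and it rules out three stronger readings that a reader might infer:

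- That the headline accuracy will come from blood. No text says which score supplies it.
- That VOCs sharing signal with blood are adjusted away and rejected. No rule selects VOCs on the adjusted coefficient, and the attenuation depends on correlations that the documents do not give.
- That the primary question goes unanswered. Section 5.1 speaks of biomarkers and does not specify a panel, so single-marker curves answer it in part.

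What the reply does not remove is the stated covariate set. The canonical VOCs are not defined, and no breath-only multivariable model is given. The added-value rationale would need blood only against blood plus breath, and 10.1 does not set that contrast either.

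**Conclusion.** The point holds in a limited form. The objective concerns breath, while the only multivariable model stated for the primary analysis always contains four blood markers. Any multi-marker accuracy from that model is that of breath plus blood and could reach 80% with little or no breath signal. This attribution problem follows from the text and needs no assumption about correlation.

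The effect on VOC coefficients is a possibility only. In the illustration it runs from none to a change of sign, under assumed accuracies, equal-variance normal scores and ρ up to 0.7.

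The single-predictor ROC curves and binary regressions reduce the mismatch for individual markers but are not stated to cover a breath panel. The objection is to something 10.1 fixes, so it does not depend on what the unseen analysis plan may add.

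**What to change.** In 10.1:

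1. Take the primary sensitivity, specificity and predictive values from a model of the breath markers without the four blood markers. If age and sex are kept, also report the model with age and sex only, so that the contribution of breath is visible.
2. Move blood eosinophils, BNP, CRP and Troponin-I to a separate pre-specified comparison of blood only with blood plus breath, reporting the change in AUC with its confidence interval. The clinical-validation objective in 5.2 is a natural home for it.

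The cost is a change of wording, one or two extra models and probably a lower headline accuracy. The first step needs no further data. For the second, check availability: as extracted, Table 1 shows no visit 2 entry for Troponin-I in any patient group and none for BNP in asthma or pneumonia, and Table 2 lists neither for children. The comparison should state which markers and participants it covers.

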The proposed program of research will identify and evaluate the diagnostic and prognostic value of exhaled breath metabolomic biomarkers in acute cardio respiratory breathlessness and common indicator diagnoses associated with acute cardio respiratory breathlessness. Specific indicator conditions have been selected according to their (i) relatively high prevalence, (ii) high unmet need, mortality and morbidity and (iii) need to develop better diagnostic and prognostic algorithms in acute care pathways.

The focus of the research program will be to phenotype using a combination of 'discovery' and near-patient care breath sampling technologies in acutely breathless patients attending two acute admissions units within Leicestershire. The indicator diagnoses of interest are (i) acute heart failure, (ii) exacerbations of adult asthma and COPD, (iii) community acquired pneumonia and (iv) paediatric exacerbations of acute childhood wheeze and confirmed asthma. Other disorders that are associated with acute breathlessness including exacerbations and acute presentations of pulmonary fibrosis, acute pulmonary embolism will not be studied within the program due to low prevalence, lack of standardised definitions and likely small sample size (pulmonary fibrosis) and adequate acute companion diagnostics (pulmonary embolism).

The program will be divided into two phases. **Phase 1**, a discovery phase to identify putative breath biomarker panels and **phase 2**, a validation phase to replicate and validate selected biomarkers within phase 1 using point of care breath sensing devices.

Patient level clinic-pathological and outcome data (spanning the entire acute pathway) will be collected in parallel to breath sampling. In addition, breath samples will be acquired during the recovery from the acute state and in the stable state post exacerbation to better understand the kinetics of breath analytes associated with these diseases.

A parallel cohort of age/home environment matched Adult/ parent/sibling/spousal healthy volunteers will also be recruited and evaluated at selected matching time points with breath analysis and a range of questionnaires to evaluate factors that are known to influence the metabolome including diet, lifestyle and the environment. Additionally patients with stable asthma, COPD and heart failure will be recruited from primary and secondary care as disease control populations.

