8.3 Study Assessments

A summary of both baseline and follow up assessments is outlined in Table 1 (adults) and Table 2 (children) below. If appropriate consent is in place the subjects may undertake any combination of any of the investigations listed in the investigation table at any of these visits.

Table 1: Summary of adult assessments

		COPD		Asthma			Pn	eumo	nia	He	art Fail	Healthy		
Time point	1a	1b	2	1a	1b	2	1a	1b	2	1a	1b	2	1a	2
Written Informed Consent	Χ			Χ			Χ			Χ			Χ	
Collection of demographic data (age, gender, height, weight,	Χ^		Χ^	Χ^		Χ^	Χ^		Χ^	Χ^		Χ^	Χ	Χ
ethnicity, smoking status)*														
Time of date of admission/discharge#	Χ^	Χ^		Χ^	Χ^		Χ^	Χ^		Χ^	Χ^			
Breathless Scores*														
Patient defined breathlessness	Χ^		Χ	Χ^		Χ	Χ^		Х	Χ^		Χ	Χ	Χ
Extended MRC dyspnoea score	Χ^		Χ^	Χ		Χ	Χ		Χ	Χ		Χ	Χ	Χ
New York Heart Association Dyspnoea Score (NYHA)										Χ^		X^		
100 mm visual analogue breathlessness score	Χ		Χ	Χ		Χ	Χ		Χ	Χ		Χ	Χ	Χ
Exacerbation history (previous health care utilisation and	Χ^		Χ^	Χ^		Χ^	Χ^		Χ^	Χ^		Χ^	Χ	Χ
acute use of medication)*														
Quality of breath VOCs questionnaire	Х	Χ	Χ	Χ	Χ	Χ	Χ	Χ	Х	Х	Χ	Χ	Χ	Х
Structured Clinical History of presenting complaint and past	Χ^		Χ^	Χ^		Χ^	Χ^		Χ^	Χ^		X^	Χ	Х
medical history*														1
Assessment of acute disease severity#*		•								•				
DECAF Score	Χ^													
CURB 65 Score							Χ^							
BTS Asthma Severity Score				Χ^										
Heart failure risk calculator										Χ^				
Concurrent medication usage	Χ^	χ^	Χ^	Χ^	Χ^	Χ^	Χ^	Χ^	Χ^	Χ^	Χ^	X^	Х	Х
12 lead ECG*	Χ^			Χ^			Χ^			Χ^				
Chest X-ray*	Χ^		Χ^	Χ^		Χ^	Χ^		Χ^	Χ^		Χ^		
Health Status Questionnaires*														
Asthma Quality of Life questionnaire (AQLQ)				Χ		Χ^								
COPD assessment tool (CAT)	Χ		Χ^											

		COPD		1	Asthma	a	Pneumonia			Hea	art Fail	Healthy		
	1a	1b	2	1a	1b	2	1a	1b	2	1a	1b	2	1a	2
NASA Task Load Index	Χ		Χ	Χ		Χ	Χ		Χ	Χ		Χ	Χ	X
Blood tests*														
BNP	Χ^		Χ	Χ			Χ			Χ^		Χ^	Χ	
Troponin-I	Χ			Χ			Χ			Χ^			Χ	
CRP	Χ^		Χ^	X^		X^	X^		X^	Χ^		Χ^	Χ)
Full blood count + differential count	Χ^		Χ^	Χ^		X^	X^		X^	Χ^		X^	Χ)
DNA and RNA (PAXGENE)~	Χ		Χ	Χ		Χ	Χ		Χ	Χ		Χ	Χ	7
Plasma and serum	Χ		Χ	Χ		Χ	Χ		Χ	Χ		Χ	Χ	- 7
Arterial or capillary blood gas*#	Χ^			Χ^			X^			Χ^				
Peripheral blood flow cytometry	Χ		Χ	Χ		Χ	Χ		Χ	Χ		Χ	Χ	
Lung function test		•												
Spirometry*	Χ^		Χ^	Χ^		Χ^							Χ	- 2
Oscillometry*	Χ		Χ	Χ		Χ	Χ		Χ	Χ		Χ	Χ	2
Exhaled nitric oxide (FeNO)				Χ		X^								

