Sputum sample (spontaneous^ or induced)	Χ^		Χ	X^		Χ	X^		Χ	X^		Χ	Χ	
Volatile organic compounds (VOCs)	Χ	Χ	Χ	Х	Χ	Χ	Χ	Χ	Χ	Х	Χ	Χ	Χ	
Urine sample*	Χ		Χ	Χ		Χ	Χ		Χ	Χ		Χ	Χ	
Echocardiography*	Х									Χ^				
Quadriceps ultrasound	Х	Х	Х											
4 meter gait speed		Χ	Χ								Χ	Χ		
Review of Adverse Events & Serious Adverse Events		Χ	Χ		Χ	Х		Χ	Χ		Χ	Χ		7
Physical Exam*	χ^		Χ^	χ^		Χ^	Χ^		Χ^	χ^		Χ^	Х	

^{*}Can be performed at time points 1a or 1b. for healthy volunteers this can be completed at visit 1 or 2. For informed consent see protocol, ^ may be part of routine clinical care according to UHL Trust Guidelines. Arterial, capillary blood gases and blood cultures only done in selected clinical cases, # Acute patients only ~If DNA taken at time point 1a will not be repeated at timepoint 2.

Table 2: Summary of children assessments

essments		hood WI firmed A	Hea	thy	
Time point	1a	1b	2	1a	2
Written Informed Consent	Х			Х	
Collection of demographic data (age, gender, height, weight, ethnicity, smoking status)*	Χ^		Χ^	Х	Х
Time of date of admission/discharge#	Χ^	X^			
100 mm visual analogue breathlessness score*	Х		Х	Х	Х
Exacerbation history (previous health care utilisation and acute use of medication)*	Χ^		Χ^	Х	Х
Quality of breath VOCs questionnaire	Χ	Х	Χ	Х	Х
Structured Clinical History of presenting complaint and past medical history*	Χ^		Χ^	Х	Х
Concurrent medication usage	Χ^	Χ^	Χ^	Х	Х
Chest X-ray*	Χ^		Χ^		
Health Status Questionnaires*					
Asthma control questionnaire (ACQ)	Χ^		Χ^		
Asthma quality of life questionnaire (AQLQ)	Χ^		Χ^		
NASA Task Load Index	Х	Х	Х	Х	Х
Blood tests*+\$					
CRP	Χ^		Χ^	Х	Х
Full blood count + differential count	Χ^		Χ^	Х	Х
DNA and RNA (PAXGENE)	Х		Х	Х	Х
Plasma and serum	Х		Х	Х	Х
Arterial or capillary blood gas*	Χ^				
Blood culture*	Χ^				
Lung function test					
Spirometry*	Χ^		Χ^	Х	Х
Exhaled nitric oxide (FeNO)	Х		Х	Х	Х
Sputum sample (spontaneous^ or induced)\$	Χ^		Χ^	Х	Х
Volatile organic compounds (VOCs)	Х	Х	Х	Х	Х
Urine sample*	Х		Х	Х	Х
Review of Adverse Events & Serious Adverse Events		Х	Х		Х
Physical Exam*	Χ^		Χ^	Х	Х

^{*}Can be performed at time points 1a or 1b. For informed consent see protocol, ^ Part of routine clinical care as part of the University Hospitals of Leicester, acute care clinical pathway. Will be performed in selected clinical cases based on clinical need, # Acute patients only, + up to 35 mls maximum per visit, ⁵ optional

A description of the research assessments is outlined below

Demographics

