All standard clinical demographics routinely recorded in acutely unwell patients will be captured using study specific case report forms (CRFs). These will include the age, sex, height, weight, smoking status and ethnicity of the patient.

Medical History

All standard clinical data routinely recorded in acutely unwell patients will be captured using study specific case report forms (CRFs). This will include co morbidities usually supplied with the GP referral letter and the use of hospital clinical information systems such as ICE to cross check co morbidities where necessary using discharge summaries as well as case notes review.

• Concomitant Medication

Current medication will be collected. This will comprise of usual medication, medication in the two weeks prior to visit 1a. In the case of admission, additional confirmation will be performed after standard pharmacy review by the admissions pharmacist allocated to the admissions unit in question.

• Physical Examination

All standard clinical data routinely recorded in acutely unwell patients will be captured using study specific electronic case report forms (CRFs). Standard clinical examination findings relevant to the indicator diagnosis in question will be recording and will include pulse, blood pressure, temperature, respiratory rate, oxygen saturations and impairment of cognition.

• Collection and recording of standard clinical care pathway diagnostic

The majority of acute care admissions with undifferentiated breathlessness will undergo various combinations of the following assessments dependent upon their admission diagnosis.

- Chest x ray
- 12 lead ECG
- Laboratory blood tests may include: Urea and electrolytes, liver function tests, albumin, corrected calcium,phosphate, D-Dimer, BNP, Troponin-I, full blood count, haematocrit and differential white cell count.
- Additional investigation such echocardiography (will be done during acute admission between time points 1a and 1b). Echo will measure LV and RV function, LA size, vavular function, LV wall thickness and e/e' on tissue Doppler.
- **The responsibility to act upon and record abnormal investigations within the patient's clinical notes will remain with the admitting clinical team who will have ordered and requested the investigations.
 - Breath sampling procedures (PLEASE REFER TO APPENDIX D: ASSET ALLOCATION APPENDIX FOR A
 DETAILED SUMMARY OF THE CORE BREATH DETECTION TECHNOLOGIES)

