8.7 Source Data

In this study a paper CRF will be collected for all 'research only' measurements defined in tables 1 and 2. The electronic CRFs will be used as the source document for the captured data fields described in Table 1 and 2 that are part of routine clinical care. The rationale for this is that data collection for routine clinical care measures within MRC EMBER is populated in to the eCRF from existing UHL IM&T systems (Figure 4 e.g. IMPAX, ilab, CODE BREAKER) as well as prospectively confirmed by the research team for relevant study clinical meta data of interest e.g. smoking status, medication.

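### The disease-class models in section 10.1 omit smoking status, which is already recorded, so a smoking-driven breath compound can pass as a class marker

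*Protocol*

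**What the plan says.** Protocol section 10.1 sets three kinds of marker model.

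- **Primary model.** The outcome is defined thus: "the outcome is a nominal variable with levels (1) Acute breathlessness (2) Recovery form acute breathlessness". Besides the metabolomic markers, the named covariates are "age, sex, standard acute care pathology markers blood eosinophils, BNP, CRP, Troponin-I, canonical VOCs extracted from breath analysis" and, where relevant, a comorbidity score.
- **Disease-class model.** The levels are heart failure, pneumonia, adult asthma/COPD and childhood wheeze/asthma. The named covariates are "age, sex, validated co morbidity scores such as the Charlson score, indicator disease risk scores such as the CURB-65 pneumonia score", then the DECAF score and acute treatments. All are conditional on improving the fit.
- **Binary logistic models** of volatile organic compounds (VOCs) against acute disease. No covariates are named.

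Smoking appears in none of these. It is, however, collected. Section 8.3 says of the demographics: "These will include the age, sex, height, weight, smoking status and ethnicity of the patient". The demographic row of Table 1 (adults) and of Table 2 (children) includes it at 1a and 2 for every disease column and for healthy volunteers. Section 8.7 gives it as an example of "relevant study clinical meta data of interest e.g. smoking status, medication".

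Section 4 says that healthy volunteers complete questionnaires on "factors that are known to influence the metabolome including diet, lifestyle and the environment". The effect of lifestyle on breath markers is otherwise only an exploratory objective (section 5.3), which adjusts no marker model.

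**The concern.** A class model compares different people. If current smoking is more common in one adult class than in the others, or in patients than in healthy volunteers, a VOC that responds to smoke and to nothing else will be associated with that class.

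Nothing in the design prevents this. Healthy volunteers are matched on age and/or home environment (section 2), and the criteria in sections 7.2 and 7.3 do not restrict smoking. The fit condition does not help either: a covariate can distort the marker coefficient and still fail a fit criterion, and smoking is not on the list of candidates.

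Replication would not expose the error. Phase 2 recruits the same classes in the same way, so an imbalance in phase 1 would be expected again. Such a marker would also miss the protocol's own standard in section 4, that a useful marker comes from the target organ and adds to existing diagnostic tools. Smoking is already known from the history.

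**Working it through.** **Inputs from the protocol.** 55 patients per adult class per phase (Appendix C, 21.5), so one class against the other three is 55 v 3 × 55 = 165. Two-sided 5% level (10.3). Target odds ratio 1.2 (Appendix C, 21.2); its unit is not stated.

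**Assumed inputs, not in the protocol.** Smoking prevalence by class, and the shift δ (in SDs of the noise) that smoking causes in the VOC. The VOC carries no disease information.

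**Central case: 40% v 15% current smokers, δ = 1.**

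1. Mean difference = δ(p₁ − p₀) = 0.40 − 0.15 = 0.25.
2. Variance in each group = 1 + δ²p(1 − p): 1 + 0.24 = 1.24 in cases and 1 + 0.1275 = 1.1275 in the others.
3. SE = √(1.24/55 + 1.1275/165) = √0.02938 = 0.171.
4. z = 0.25/0.171 = 1.46.
5. Rejection probability = Φ(1.46 − 1.96) + Φ(−1.46 − 1.96) ≈ 0.31, against a nominal 0.05.
6. Apparent odds ratio: the pooled within-group variance is (55 × 1.24 + 165 × 1.1275)/220 = 1.156. The slope is about 0.25/1.156 = 0.216 per unit. The overall SD is √(1.156 + 0.25 × 0.75 × 0.25²) = 1.080, so the slope per SD is 0.234 and the odds ratio is about 1.26.

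Two logistic simulations agree: one gave an odds ratio of 1.27 per SD, the other 1.26 with 29% rejections.

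**Range (simulated, 55 v 165, 1,000 studies each).**

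| Smokers, class v rest | Shift | Apparent OR per SD | Rejections, smoking omitted | Rejections, smoking included |
|---|---|---|---|---|
| 20% v 20% | 1 / 2 SD | 1.00 / 1.00 | 5% / 4% | 5% / 6% |
| 30% v 15% | 1 / 2 SD | 1.15 / 1.27 | 13% / 34% | 5% / 4% |
| 40% v 15% | 1 / 2 SD | 1.26 / 1.48 | 29% / 69% | 5% / 5% |
| 50% v 10% | 1 / 2 SD | 1.47 / 1.90 | 68% / 97% | 6% / 5% |

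A milder case, 40% v 25% with δ = 0.5, gives an odds ratio of 1.08 and 8% rejections.

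**Primary model (simulated, the same 220 patients acute and recovered, 1 SD shift).** With 30% smoking at both visits the rejection rate is 3%, so there is no inflation. With active smoking at 20% acute v 30% recovery it is 14%; at 10% v 30% it is 51%.

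**The case against.** Several counter-arguments have force.

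- **The primary analysis.** A reader might infer that the primary result is confounded too. The documents do not support that. Acute and recovery samples come from the same patients, so a smoking status that does not change largely cancels. Bias needs a change in active smoking between visits, for example abstinence in hospital, and the protocol has no data on this. A current/ex/never item might not capture it either, since an abstaining inpatient may still be recorded as current.
- **Assumed inputs.** No prevalence or VOC effect is given, and section 4 speaks of lifestyle, not smoking by name. That smoking differs between the classes is a plausible premise, not a stated fact. The illustration runs from almost nothing to very large.
- **Diagnostic purpose.** The primary objective is sensitivity, specificity and predictive values. Covariate adjustment changes association odds ratios; it leaves a single marker's unadjusted ROC curve as it was. This is correct, and it is why adjustment alone is not enough.
- **Deferral.** Section 10.1 sends detailed methods to a data analysis plan that is not shown and that may add smoking. The term canonical VOCs is undefined and might include smoking-related compounds. But the protocol itself names the covariates, so its list can be reviewed as it stands.
- **Coverage.** A reader might take smoking to be recorded for every participant. Table 1 has no column for the stable-disease group, so this is shown only for the tabulated groups.
- **Recoverability.** The study calls itself exploratory (10.2), and the adjustment can still be added before analysis.

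**Conclusion.** The point stands for the adult disease-class models and for the binary VOC models, including those against healthy volunteers. As written, nothing in section 10.1 separates a smoking effect from a class effect, although the variable is on file. Under the central assumptions the apparent odds ratio of about 1.27 exceeds the 1.2 that the study is sized to detect (if that is also per SD), and about 30% of studies would flag a null VOC. With equal smoking prevalence the rate is about 5%, so the problem depends entirely on imbalance between the groups. Including smoking returns the rate to 4–6% in every simulated class scenario.

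A bias in the primary acute-versus-recovery model is not shown. There, smoking belongs in a sensitivity analysis.

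**What to change.** In section 10.1, and in the data analysis plan to match:

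1. Include smoking status, as recorded at the breath-sample visit, as a covariate in the adult class-discrimination models and in the binary VOC–disease models, including those against healthy volunteers. Exempt it from the model-fit condition.
2. Repeat the marker analysis, including ROC curves, sensitivity and specificity, in participants who are not current smokers. This addresses the accuracy measures, which adjustment does not change.
3. For the primary acute-versus-recovery model, add smoking as a sensitivity analysis only.
4. Do not extend the exemption to age in any model that contains the paediatric level. Children are 5–15 and adults 16 or above (7.2), so age separates that level perfectly and ordinary maximum-likelihood estimates would not exist.

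**Cost.** No new data field for the tabulated groups, and a short addition to the text. Smoking takes one parameter per contrast (current v not current) or two (current, ex, never). Under the 20:1 rule in 10.2, a class of 55 supports 55/20 = 2.75 variables and a class of 100 supports 5. At 55, the two-level coding leaves 1.75 and the three-level coding 0.75, so the two-level coding is preferable at the minimum class size. The analysis restricted to participants who are not current smokers will be smaller and less precise.
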